I, the undersigned declare that I have reviewed the statistical analysis plan along with TLF mockups and that to the best of my knowledge the document is internally consistent with protocol and scientifically rational. Reviewed by:

Signature:

Title: Project Manager

Organization: ICON plc

AUTHORIZATION: I, the undersigned, declare that I have reviewed the statistical analysis plan along with TLF mock-ups and that to the best of my knowledge the document accurately reflects the protocol objectives.

Authorized by:

Signature:

Title: Global Medical Statistician

Organization: Sanofi

CONFIDENTIAL Page 4 of 30

REVISION HISTORY

Version	Date	Author	Reasons
1.0	DEC 08, 2021		Initial Version.
2.0	SEP 12, 2022		Modification of the NRS response definition in the "Section 5.1.7.1 Primary analysis".
			Modification of the "Section 5.1.7.4.2 Use of rescue medication" to detail its definition and new protocol version with revised enrolment criteria.
3.0	DEC 01, 2022		Analysis Timepoints update according to the Memo to File (NTF 019 dated 22NOV2022).
			Addition of sensitivity analysis and corresponding Sensitivity Analysis Population.
			Addition of Full Analysis Set.
			Addition of MedDRA and WHO drug dictionary versions.
4.0	DEC 12, 2022		Modification of mITT, FAS, and Sensitivity Analysis Populations.
			Modification of the Time to Reach Acceptable Pain definition.
			Modification of Time-to-event endpoints analysis.
			Implementation of the analysis by actual treatment group for the Safety Population.

CONFIDENTIAL Page 5 of 30

LIST OF ABBREVIATIONS

Abbreviation or special term	Explanation
AE	Adverse Event
ANCOVA	Analysis of Covariance
CI	Confidence Intervals
CRF	Case Report Form
CTMS	Clinical Trials Management System
EOS	End of Study
EOT	End of Treatment
ET	Early Termination
FAS	Full Analysis Set
IA	Interim Analysis
ICF	Informed Consent Form
IQR	Inter Quartile Range
ITP	Infrared Therapy Patches
ITT	Intent-to-Treat
LS Means	Least-Square Means
MedDRA	Medical Dictionary for Regulatory Activities
mITT	Modified Intent-to-Treat
NRS	Numerical Rating Scale
NTF	Note to File
PAR	Pain Relief Score
PD	Protocol Deviation
PID	Pain Intensity Difference
PT	Preferred Term
Q1	First Quartile
Q3	Third Quartile
RMDQ	Roland-Morris Disability Questionnaire
SAE	Serious Adverse Event
SAP	Statistical Analysis Plan
SD	Standard Deviation
SDTM	Study Data Tabulation Model
ONFIDENTIAL	Page 6 of 30

Abbreviation or special term	Explanation
SDTMIG	Study Data Tabulation Model Implementation Guide
SE	Standard Error
SI	International System
SOC	System Organ Class
SPID	Sum of Pain Intensity Difference
TEAE	Treatment-Emergent Adverse Event
TEAE	Treatment-Emergent Adverse Event
TFLs	Tables, Listings, and Figures
TOTPAR	Total Pain Relief
TTAP	Time to Reach Acceptable Pain
TTNP	Time to Reach No Pain
UADE	Unanticipated Adverse Device Effect
WHODRUG	World Health Organization Drug Dictionary

CONFIDENTIAL Page 7 of 30

Private and Confidential Study No LPS16453 Date: DEC 12, 2022

1 INTRODUCTION

This statistical analysis plan (SAP) describes the statistical methods and data handling methods to be followed during the final reporting and analyses of data collected for the study Protocol LPS16453.

This SAP should be read in conjunction with the study protocol, case report form (CRF), e-diary Data Export Specification and corresponding Mapping Specification. This version of the plan has been developed using protocol version 4 dated 22JUL2022, CRF version 4.0 dated 30AUG2022and e-diary Data Export Specification – Lunexis Engage version 2.0 dated 26JUL2021 along with associated Mapping Specification version 2.0 dated 26JUL2021.

CONFIDENTIAL Page 8 of 30

2 STUDY DETAILS

2.1 Study Objectives

2.1.1 Primary Objective

The Primary objective of the study is to assess the efficacy of the ITP FIRTECH for treating subjects suffering from mild to moderate acute low back pain.

2.1.2 Secondary Objectives

The Secondary objectives of this study are listed below:

- 1. to assess the efficacy of ITP FIRTECH on the subject disability;
- 2. to assess the efficacy of ITP FIRTECH on the degree of subject mobility;
- 3. to assess the safety of ITP FIRTECH.

2.1.3 Exploratory Objectives

Exploratory objectives for this study include:

- 1. to assess the frequency and use of rescue medication;
- 2. to assess the subject evaluations of least, average, and worst pain.

2.2 Study Endpoints

2.2.1 Primary Endpoint

A Numerical Rating Scale (NRS) responder at Day 5 at the on-site evaluation (defined as $\geq 30\%$ decrease from baseline of the instantaneous pain and no rescue medication).

2.2.2 Secondary Endpoints

The Secondary endpoints of this study are listed below:

- 1. normalized Sum of Pain Intensity Difference (PID, which equals the instantaneous NRS change from baseline) over 5 days (SPID₀₋₅);
- 2. Roland-Morris Disability Questionnaire (RMDQ) score improvement (%) from baseline to Day 5;
- 3. mobility evaluation: change from baseline to Day 5;
- 4. time to reach acceptable pain;
- 5. time to reach no pain (NRS = 0);
- 6. time course of PID over time from baseline to Day 5 on-site evaluation;
- 7. time course of Pain relief over time from baseline to Day 5 (VRS);
- 8. normalized Sum of Pain relief over 5 days (TOTPAR₀₋₅).

2.2.3 Exploratory Endpoints

Exploratory objectives for this study include:

- 1. frequency of use of rescue medication;
- 2. description of "worst pain" evaluation;
- 3. description of "least pain" evaluation;

CONFIDENTIAL Page 9 of 30

4. description of "average pain" evaluation.

2.2.4 Safety Endpoints

[figure not shown]
Safety endpoints will include:

- 1. incidence of Adverse Events;
- 2. incidence of Serious Adverse Events;
- 3. incidence of Treatment Emergent Adverse Events.

2.3 Study Design

This is an open label, randomized, proof-of-concept clinical trial, comparing the ITP FIRTECH with a no-patch control arm. The study will be performed in Medical Centres and an online e-diary will be used. A total of 2 site visits and 1 phone contact are planned during a maximum of 6 days of study duration, as shown in Figure 1. Details on the schedule of events are provided in Table 1.

Figure 1. Study Schema

Day 1	Day 1 to Day 5	Day 5	Day 6
At Study Center: *Subject enrollment *e-diary activation *Baseline assessments	At Home *Diary completion	*On-site assessments *Patch removal	End of Study Discharge
*Randomization *Patch application for Arm A			

CONFIDENTIAL Page 10 of 30

Table 1. Schedule of Events

Visits	V1	At Home	V2	Phone Call	Unsch	Notes
Days	D1	D1 to D5	D 5	D 6		Notes
Eligibility verification	✓					
Informed Consent	✓					
Demographics / Medical History	✓					
Physical Exam	✓		✓		✓	
Vital Signs	✓				✓	
Urine Pregnancy Test	√					For women of child-bearing potential only
E-diary Activation	✓					
Randomization	✓					
E-diary Completion	√	√ *	√ **			*2 times per day at the same times **On-site evaluations
Pain perception	✓	✓	✓			
Pain-relief evaluation		✓	✓			
Pain acceptable perception		√	√			
Rescue Medication Needed		✓	√			
Roland-Morris Disability Questionnaire	√		√			
Mobility assessment	√		√			Schober's Test or Fingertip- to- floor test
Adverse Event assessment	√	√	√	✓	✓	
Patch application / removal	✓		V		V	Patch(es) has(have) to be used for 5 days. If the patch is taken-off for a safety reason, the subject has to contact the study center. If the patch falls off, the subject has to replace it as soon as possible. The subject will complete the diary card, informing about the patch replacement, the reason of change, and the time spent with no patch.
Concomitant therapies	✓	✓	✓	✓	✓	
e-diary review			✓		✓	

CONFIDENTIAL Page 11 of 30

2.4 Determination of Sample Size

The efficacy of the patch will be assessed compared with no-patch use. The primary endpoint is the occurrence of being a NRS-responder at Day 5 defined as ≥ 30% decrease from baseline of the instantaneous pain and no rescue medication. The responder proportion in the "no-patch" arm is unknown, and a variety of proportions of responders are envisaged. The targeted treatment effect size is medium (Cohen's H ranging from 0.42 to 0.45). Ninety evaluable subjects per group (180 evaluable subjects in total) are needed to reach 80% power, as shown in the following table.

Table 2. Power Calculations

N non Croun	Alpha	Respon	Cohen's H	
N per Group	(2 sided)	No Patch	Patch	Collell's H
90	5%	10%	27%	0.449
90	5%	20%	39%	0.422
90	5%	30%	51%	0.432
90	5%	40%	61%	0.423
90	5%	50%	71%	0.433
90	5%	60%	80%	0.422

Further assuming a dropout rate of 10%, the expected number of subjects to be randomized is a total of 200. Subjects will be randomized 1:1 to the treatment and no patch arms. The estimated number to be screened to achieve 200 randomized subjects is 260.

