6.4.1 Sample Size

The efficacy of the patch will be assessed compared with no-patch use. The primary endpoint is the occurrence of being a NRS-responder at Day 5 defined as \geq 30% decrease from baseline of the instantaneous pain and no rescue medication. The responder proportion in the "no-patch" arm is unknown, and a variety of proportions of responders are envisaged. The targeted treatment effect size is medium (Cohen's H ranging from 0.42 to 0.45). Ninety evaluable subjects per group (180 evaluable subjects in total) are needed to reach 80% power, as shown in the following table.

Alpha N per Group **Responder Rate** Cohen's H (2 sided) No Patch Patch 90 5% 10% 27% 0.449 90 5% 20% 39% 0.422 90 5% 30% 51% 0.432 90 5% 40% 61% 0.423 90 5% 50% 71% 0.433 90 0.422 5% 60% 80% Powers are calculated using East 6.4

Table 2. Power Calculations

Further assuming a dropout rate of 10%, the expected number of subjects to be randomized is a total of 200. Subjects will be randomized 1:1 to the treatment and no patch arms. The estimated number to be screened to achieve 200 randomized subjects is 260.

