8.3.1 Efficacy Analyses

8.3.1.1 Primary Analysis

Descriptive analysis will be conducted for the instantaneous pain on NRS (A Numerical Rating Scale^[3]). The summary statistics will be presented for observed values at Day 5 and change from baseline to Day 5 for each group (patch, no-patch).

The rate of NRS-responders at Day 5 where NRS-response is defined as \geq 30% decrease from baseline of the instantaneous pain and no rescue medication will be presented descriptively for each group (patch, no-patch), along with an associated 95% confidence interval.

The hypothesis that there is no difference in the rate of responders will be tested between the group with patch and no-patch group at Day 5 using Fisher's exact test and presented with its associated p-value.

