3.3 General guideline for inferential analysis

All statistical tests will be conducted at 2-sided using 5% alpha level.

The inferential analysis of quantitative variables based on analysis of covariance (ANCOVA) model with the treatment group as fixed effect and baseline instantaneous pain NRS as a continuous covariate will be conducted with estimating and providing the Least-Square Means (LS Means), Standard Errors (SE) and 95% Confidence Intervals (CI) for each treatment group along with the LS Means, SE and 95% CI for the difference between treatment groups. Additional effects will be added to the model in case of need and described in CSR.

The inferential analysis of time-to-event endpoints will include summary, survival curves, and analysis using Kaplan-Meier estimation method. The comparison of survival distributions between treatment groups will be done by the Log-Rank test.

The inferential analysis of key secondary endpoints will be adjusted for multiplicity using a False Discovery Rate approach (Benjamini-Hochberg) within a separate analysis table that will consist nominal and adjusted p-values. Tables with original inferential key secondary analyses will be presented with the nominal p-values.

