5.1.7 Efficacy Analysis

5.1.7.1 Primary Analysis

Instantaneous pain on NRS will be summarized for actual values and change from baseline with descriptive statistics for the ITT and FAS populations by treatment group and by analysis timepoint (from Baseline to Day 5 Visit 2).

NRS-response will be defined as $\geq 30\%$ decrease from the baseline of the instantaneous pain and no rescue medication (Section 5.1.7.4.2).

CONFIDENTIAL Page 19 of 30

The number and percentage of NRS-responders at Day 5 Visit 2 will be presented descriptively by treatment groups, along with associated 95% confidence intervals.

The difference in the rate of responders at Day 5 Visit 2 will be tested between treatment groups using two-sided Fisher's exact test at the 5% error level (alpha = 0.05) and presented with its associated p-value. The null hypothesis H_0 that there is no difference in the rate of responders will be tested against the alternative hypothesis H_A that there is a difference in the rate of responders:

$$H_0: p_T - p_C = 0$$

$$H_A: p_T - p_C \neq 0$$

Where p_T denote the rate of responders at Day 5 Visit 2 in the FIRTECH Patch treatment group (treatment, T) and p_C denote the rate of responders at Day 5 Visit 2 in the No Patch treatment group (control, C). This analysis will be based on the mITT population.

A sensitivity analysis will be conducted by executing the primary endpoint analysis for subjects from the Sensitivity Analysis population. A list of subjects excluded from the Sensitivity Analysis population will be provided along with the reason for their exclusion.

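### At 90 evaluable subjects per group the planned Fisher's exact test has about 75–81% power, not 80% in every scenario, and the test behind the power table is not named

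*SAP*

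**What the plan says.** Protocol 6.4.1 and SAP 2.4 make the same statement: "Ninety evaluable subjects per group (180 evaluable subjects in total) are needed to reach 80% power, as shown in the following table". Table 2 in each document lists six pairs of responder rates (no patch vs patch) at 90 per group and two-sided 5% alpha, with Cohen's h for each pair. It has no power column. Both sections say that the no-patch rate is unknown, so no row is singled out as the expected one.

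On method, the protocol says only "Powers are calculated using East 6.4", which is software and not a test. The SAP table names neither.

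The primary test is fixed elsewhere. SAP 5.1.7.1 compares responder rates "using two-sided Fisher's exact test at the 5% error level (alpha = 0.05"), and protocol 8.3.1.1 compares them "at Day 5 using Fisher's exact test and presented with its associated p-value". No other test is given for the primary endpoint.

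The step from evaluable to randomized subjects is: "Further assuming a dropout rate of 10%, the expected number of subjects to be randomized is a total of 200".

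**The concern.** A power figure belongs to a particular test. Fisher's exact test is conservative, so a sample size that just gives 80% with an uncorrected chi-square or normal test will usually give less with Fisher's test. Here the sizing test is unnamed and the table prints no power, so a reader cannot tell whether the 80% refers to the planned analysis.

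That 80% is the only justification offered for the sample size. If it does not hold for the planned test, the chance of missing the targeted effect is understated. This matters most when a non-significant result has to be interpreted. Type I error is not at stake.

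**Working it through.** **Inputs.** From protocol 6.4.1 and SAP 2.4: 90 per group, two-sided alpha 0.05, six rate pairs, 1:1 allocation, 10% dropout. From SAP 5.1.7.1: two-sided Fisher's exact test at 0.05.

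**Step 1: reproduce the plan's 90.** Use the pooled normal formula without continuity correction, with p̄ the mean of the two rates:

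n = [1.960·√(2p̄(1−p̄)) + 0.8416·√(p₁(1−p₁) + p₂(1−p₂))]² / (p₂−p₁)²

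For 20% vs 39%, p̄ = 0.295:
- first term: 1.960 × √0.41595 = 1.264
- second term: 0.8416 × √0.3979 = 0.531
- n = (1.795)² / 0.0361 = 89.25, rounded up to 90

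The six rows need 81, 90, 85, 88, 84 and 82. The largest is exactly 90, and at 90 per group this formula gives at least 80% in every row. The continuity-corrected formula needs 93, 100, 94, 98, 94 and 91, so it does not reproduce 90. The dropout step is correct: 180 / 0.90 = 200.

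**Step 2: power of the planned test.** For each of the 91 × 91 possible outcomes with 90 per arm, compute the two-sided Fisher p-value, mark it as a rejection if p ≤ 0.05, and sum the product of the two binomial probabilities over the rejections. Defining the two-sided p-value by minimum likelihood or by doubling the smaller tail gives the same results.

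| No patch / patch | Pooled normal power, n = 90 | Fisher power, n = 90 | Gap to 80% | n per group for 80%, Fisher |
|---|---|---|---|---|
| 10% / 27% | 84.2% | 80.5% | none | 90 |
| 20% / 39% | 80.3% | 76.1% | 3.9 | 99 |
| 30% / 51% | 82.4% | 78.9% | 1.1 | 95 |
| 40% / 61% | 81.0% | 75.2% | 4.8 | 97 |
| 50% / 71% | 82.7% | 79.4% | 0.6 | 94 |
| 60% / 80% | 83.9% | 80.2% | none | 90 |

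Over a grid of common rates, the largest true type I error of Fisher's test at 90 per arm is 3.69%.

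**Step 3: does the margin in 200 randomized cover the gap?** Only if losses are well below the assumed 10%.
- At 95 evaluable per group (5% lost), power is 83.1, 78.5, 80.1, 79.1, 80.5 and 82.4%; two rows are still short.
- At 100 per group (none lost), it is 85.0, 80.7, 83.2, 82.7, 83.3 and 84.4%.
- All six rows first reach 80% at 99 per group. With 10% dropout that means 198 / 0.90 = 220 randomized.

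**Step 4: Cohen's h.** h = 2·arcsin√p₂ − 2·arcsin√p₁. The first five rows give 0.449, 0.422, 0.432, 0.423 and 0.433, as printed. For 60% vs 80%, h = 2.2143 − 1.7722 = 0.442; both documents print 0.422. The correct value lies within the stated 0.42–0.45 range and affects neither the sample size nor the power.

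**The case against.** The strongest counter-argument concerns the discreteness of Fisher's test. Exactly equal arms are an unfavourable case, and the primary population (mITT, SAP 4.1.2) will rarely split 90/90. Keeping 180 evaluable subjects but shifting one or two between arms gives, in table order:

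| No patch / patch n | 10/27 | 20/39 | 30/51 | 40/61 | 50/71 | 60/80 |
|---|---|---|---|---|---|---|
| 89 / 91 | 82.4 | 78.4 | 81.3 | 77.2 | 80.5 | 81.7 |
| 91 / 89 | 83.3 | 77.9 | 80.0 | 77.6 | 81.8 | 82.2 |
| 88 / 92 | 83.9 | 77.1 | 80.7 | 76.9 | 81.2 | 82.8 |
| 92 / 88 | 81.7 | 79.0 | 80.6 | 77.2 | 81.1 | 81.0 |

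This is right, and it removes the small misses at 30/51 and 50/71 (79.98% in one cell). It does not remove the other two: 20/39 and 40/61 stay at 77–79% in all four splits, short by about 1–3 points. The documents also state their claim for 90 per group, so that is the case to check.

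It is also fair to say that:
- 90 is not a miscalculation if the sizing test was an uncorrected one;
- the gap is small against the uncertainty in the assumed rates, since with 90 per arm power returns to 80% if the patch rate is 40.0% instead of 39%, or 62.2% instead of 61%;
- the trial is described as proof-of-concept.

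These points limit the consequence. They do not make the printed statement true of the planned test.

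**Conclusion.** The concern holds. With 90 evaluable subjects per group, the planned two-sided Fisher's exact test has 75.2–80.5% power across the six scenarios. It falls below 80% in four of them, two clearly (76.1% and 75.2%). In those two rows the chance of missing the targeted effect is 24–25%, against the 20% implied. With slightly unequal arms totalling 180 it is about 21–23%.

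These figures assume the table's responder rates, independent binomial outcomes and, for the main figures, exactly 90 per arm. That the sizing used an uncorrected large-sample test is an inference from the match at 90; the documents do not settle it. The validity of the primary analysis is unaffected. What is wrong is a planning statement that does not describe the planned test, plus one misprinted effect size. It should be fixed.

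**What to change.** In both protocol 6.4.1 and SAP 2.4:

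1. Name the test used in the East 6.4 calculation.
2. Add a power column to Table 2 for the planned two-sided Fisher's exact test, labelled as holding for exactly 90 per arm: 80.5, 76.1, 78.9, 75.2, 79.4 and 80.2%. Replace the claim that 90 per group reaches 80% power with a statement that it gives about 75–81% power, depending on the responder rates.
3. Correct Cohen's h in the 60% / 80% row from 0.422 to 0.442.

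The primary test, its code and the number of subjects stay as they are. The cost is two sentences, one table column and one table entry, and a stated power that is slightly less favourable.

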2.5 Randomization

Subjects will be randomized 1:1 to the investigational patch and no patch arms.

2.6 Blinding

This is an open label study, therefore there are no blinding / unblinding procedures.

CONFIDENTIAL Page 12 of 30

3 DATA ANALYSIS CONSIDERATION

3.1 General Considerations

The statistical analyses will be performed using SAS Version 9.4 (or higher). All tables, figures and listings will be produced in landscape format.

Data will be presented at each scheduled timepoint (nominal time), where applicable.

Unless otherwise specified, the baseline will be defined as the last non-missing assessment prior to patch application (FIRTECH Patch) or randomization (No Patch) at Day 1 Visit 1.

The change from baseline will be calculated as the following:

Change from Baseline
$$=$$
 (Observed Value) $-$ (Baseline Value).

The percent change from baseline will be calculated as the following:

Percent Change from Baseline (%) =
$$\frac{(Observed\ Value) - (Baseline\ Value)}{(Baseline\ Value)} * 100\%.$$

The total number of subjects in the study group (N) under the stated set of subjects will be displayed in the header of summary tables.

All study data will be included in the study data listings. Listings will be displayed by subject in chronological order, if not stated otherwise.

For tabulated summaries, only the scheduled visits will be included in the summary tables. Unscheduled assessments will be listed.

Medications will be coded with the WHO drug dictionary (WHO Drug global B3 September 2021). Medical History, Adverse Events, and Non-drug therapies will be coded using Medical Dictionary for Regulatory Activities (MedDRA, version 24.1). The dictionary versions will remain the same throughout the course of the study.

3.2 General guideline for descriptive summaries

For continuous variables, n mean, median, standard deviation, first quartile (Q1), third quartile (Q3), inter quartile range (IQR), minimum and maximum will be presented for each treatment group and category.

For categorical variables, count and % of subjects/counts in each treatment group and/or category will be presented. Percentages will be based on the number of subjects with non-missing values, if not specified otherwise.

CONFIDENTIAL Page 13 of 30

3.3 General guideline for inferential analysis

All statistical tests will be conducted at 2-sided using 5% alpha level.

The inferential analysis of quantitative variables based on analysis of covariance (ANCOVA) model with the treatment group as fixed effect and baseline instantaneous pain NRS as a continuous covariate will be conducted with estimating and providing the Least-Square Means (LS Means), Standard Errors (SE) and 95% Confidence Intervals (CI) for each treatment group along with the LS Means, SE and 95% CI for the difference between treatment groups. Additional effects will be added to the model in case of need and described in CSR.

The inferential analysis of time-to-event endpoints will include summary, survival curves, and analysis using Kaplan-Meier estimation method. The comparison of survival distributions between treatment groups will be done by the Log-Rank test.

The inferential analysis of key secondary endpoints will be adjusted for multiplicity using a False Discovery Rate approach (Benjamini-Hochberg) within a separate analysis table that will consist nominal and adjusted p-values. Tables with original inferential key secondary analyses will be presented with the nominal p-values.

